## 2.2 Name and Description of the Investigational Agent

Bardoxolone methyl, an investigational drug, has been shown to activate the Keap1-Nrf2 system, which allows Nrf2 to increase expression of antioxidant and cytoprotective genes and decrease expression of pro-inflammatory NF- $\kappa$ B target genes (Lee, 2009; Dinkova-Kostova, 2005; Rojas-Rivera, 2012; Osburn & Kensler, 2008). Consistent with this activity, bardoxolone methyl and analogues suppress proinflammatory cytokines and chemokines and reduce oxidative stress in many cell types in response to a variety of inflammatory triggers (Chen 2015; Thimmulappa, 2007; Pei, 2019, Nichols, 2009). Approximately 3200 individuals have been exposed to bardoxolone methyl in clinical trials, including studies in patients with cancer, chronic kidney disease (CKD), and pulmonary hypertension (PH).

### 2.2.1 Preclinical Data

The potent anti-inflammatory effects of bardoxolone methyl in cultured cells has translated into broad protective activity in animal models of acute lung injury and inflammation (Nichols, 2009, Chen 2015, Pei, 2019; Reddy, 2009; Zhang, 2019; Nagashima, 2019; Kulkarni, 2013). Bardoxolone methyl and analogs

CONFIDENTIAL

This material is the property of the NYU School of Medicine and Langone Medical Center. Do not disclose or use except as authorized in writing by the study sponsor

significantly reduce neutrophil and macrophage infiltration and suppress proinflammatory cytokine and chemokine levels in the lungs of mice treated with inflammatory stimuli (Nichols, 2009; Chen 2015, Reddy, 2009). In these models, bardoxolone methyl and analogs also reduced pulmonary edema, decreased lung injury scores, prevented fibrosis, and improved lung function (Chen 2015; Pei, 2019; Kulkarni, 2013). Bardoxolone methyl and analogues also reduce proinflammatory cytokines and chemokines, prevent organ damage (lung, liver, and pancreas), and increase survival in models of systemic inflammation (Thimmulappa, 2006; Auletta, 2010, Osburn, 2008; Keleku-Lukwete, 2015; Robles, 2016).

In addition to their anti-inflammatory and tissue protective activity, bardoxolone methyl and analogs have been shown to inhibit viral replication, suppress viral infection, inhibit transcription of viral genes, and prevent latent viral reactivation *in vitro* (Vázquez, 2005; Shao, 2016; Chandra, 2018; Patra, 2019; Nio, 2019; Wyler, 2019; Rothan, 2019). Consistent with the mechanism of action of these compounds, the Nrf2 target heme oxygenase-1 (HO-1) has been shown to exhibit significant antiviral activity (Espinoza, 2017).

Lastly, preclinical studies have demonstrated that bardoxolone methyl and analogues protect kidney tissue, reduce inflammation, prevent fibrosis, and increase kidney function in many different animal models of kidney disease, including: ischemia-reperfusion-induced acute kidney injury (AKI) (Liu, 2014), chemically induced acute kidney injury (AKI) (Tanaka, 2008; Aleksunes, 2010; Wu, 2014), CKD associated with diabetes and/or obesity (Chin, 2013; Tan, 2014; Camer, 2016), CKD caused by nephron loss (Aminzadeh, 2013; Aminzadeh, 2014; Son, 2015), CKD caused by glomerulonephritis (Nagasu, 2019), autoimmune-associated kidney disease (Wu, 2014), and hypertension-associated kidney disease (Hisamichi, 2018).

## 2.2.2 Clinical Data to Date

Approximately 3200 individuals have been exposed to bardoxolone methyl in clinical trials, including studies in healthy subjects, patients with cancer, pulmonary hypertension (PH), and various forms of chronic kidney disease (CKD). As described in Section **Error! Reference source not found.**, bardoxolone methyl has been shown to improve kidney function—assessed using a variety of measures including measured inulin clearance, creatinine clearance, and estimated glomerular filtration rate—in patients with CKD due to diabetes, Alport syndrome, autosomal dominant polycystic kidney disease (ADPKD), IgA nephropathy (IgAN), and focal segmental glomerular sclerosis (FSGS) (Pergola, 2011; de Zeeuw, 2013).

The profile of eGFR increases with bardoxolone methyl reflects its multiple protective and anti-inflammatory effects. Early improvements in eGFR evident within the first 4 weeks of bardoxolone methyl treatment are likely attributed to the reversal of acute, dynamic inflammation-mediated processes such as endothelial dysfunction and mesangial cell contraction resulting in glomerular filtration surface area increases (Aminzadeh, 2013; Chin, 2018; Ding, 2013; Ferguson, 2010).

Please refer to the Investigator's Brochure for a detailed discussion of safety findings for studies in healthy subjects, cancer, CKD, and PH patients with bardoxolone methyl.

## 2.2.3 Dose Rationale (if applicable)

Several dose-ranging studies which have been conducted with bardoxolone methyl demonstrated that changes in eGFR are dose-dependent. The 20 mg bardoxolone methyl dose used in the present study provides near-optimal pharmacological activity and efficacy while also minimizing potential tolerability issues. Furthermore, most of the available clinical safety and efficacy data for bardoxolone methyl has been collected with the 20 mg dose.

## 2.3 Rationale

Some patients with moderate-to-severe COVID-19 rapidly develop symptoms that lead to serious complications such as ARDS, AKI, and multiple organ failure. The severity of COVID-19, as well as the development of serious complications, is associated with an imbalance in the response of the immune system to the infection with excessive production of pro-inflammatory cytokines and chemokines.

Bardoxolone methyl and analogues exhibit potent anti-inflammatory activity *in vitro*. Moreover, bardoxolone and analogues suppress inflammation and tissue damage in animal models of acute lung injury and reduce mortality in models of systemic inflammation. In addition to the anti-inflammatory and tissue protective

CONFIDENTIAL

This material is the property of the NYU School of Medicine and Langone Medical Center. Do not disclose or use except as authorized in writing by the study sponsor

effects, bardoxolone methyl and analogues have been shown to possess potent antiviral activity. AKI is a serious complication of COVID-19 and frequently occurs in patients with severe symptoms. Bardoxolone methyl protects the kidney in several animal models of CKD and AKI and improves kidney function in patients with diabetes, Alport syndrome, ADPKD, IgAN, and FSGS. Thus, the collective data suggest bardoxolone methyl may reduce the excessive production of cytokines and chemokines and prevent ARDS and AKI in patients with COVID-19.

## **2.4 Potential Risks & Benefits**

### **2.4.1 Known Potential Risks**

Please refer to the Investigator's Brochure for a detailed discussion of safety findings for studies conducted with bardoxolone methyl in healthy subjects or patients with cancer, CKD, or PH.

#### **2.4.1.1 Fluid Overload**

Similar to endothelin receptor antagonists (ERAs) in certain patient populations, including bosentan in advanced congestive heart failure and avosentan in advanced CKD, bardoxolone methyl treatment was found to be associated with an increased risk for fluid overload and heart failure hospitalizations in the BEACON trial, which enrolled patients with Stage 4 CKD (eGFR 15 to 29 mL/min/1.73 m^2) and type 2 diabetes (Chin, 2014). The overall increased risk for fluid overload and heart failure events with bardoxolone methyl appeared to be limited to the first three to four weeks after initiation of treatment. Patients with fluid overload events who were treated with intravenous diuretics generally resolved their symptoms. Elevated BNP and prior hospitalization for heart failure were identified as risk factors that contributed to increased risk for these events. For patients without these baseline characteristics, the risk for heart failure events among bardoxolone methyl- and placebo- treated patients was similar (2%) (Chin, 2014). The increased risk for these events from bardoxolone methyl treatment had also not been observed in six previous CKD studies, which were conducted mostly in patients with Stage 3b CKD (eGFR of 30 to 44 mL/min/1.73 m^2), patients with hepatic dysfunction or cancer, or healthy volunteers.

Subsequent studies, enrolling over 1500 patients, have employed risk mitigation procedures to reduce the potential for bardoxolone methyl-induced fluid overload. These procedures excluded patients with the identified risk factors and ensured close monitoring for fluid retention within the first month of treatment. Since these exclusions have been applied, no increased risk for acute fluid overload AEs with bardoxolone methyl has been observed. As such, BARCONA will exclude patients with known left ventricular ejection fraction (LVEF) <40% or prior hospitalization for heart failure to mitigate this risk.

#### **2.4.1.2 Transaminase and Gamma-glutamyl Transpeptidase (GGT) Elevations**

In clinical studies of bardoxolone methyl, almost all patients had increases of transaminase enzymes above baseline upon initiation of treatment, which followed a consistent pattern. These increases were not associated with elevations in bilirubin or other signs of liver toxicity. In BEACON, fewer hepatobiliary SAEs were observed in the bardoxolone methyl arm than in the placebo arm. The elevations begin immediately after initiation of treatment or an increase in dose; they peak approximately two to four weeks later. In most patients, transaminase elevations were mild, but approximately 4% to 11% of patients experienced an elevation greater than 3X the ULN. The elevations resolved to levels less than the ULN in most all patients with elevations, within two weeks after peak values while patients continued taking study drug. Patients who experienced elevations to greater than 3X the ULN sometimes required additional time to resolve. While some patients have had elevations to above 3X the ULN, persistent elevations to above 3X the ULN have not been observed, and the elevations did not recur once resolved, unless caused by other factors.

Bardoxolone methyl regulates GGT, a known Nrf2 target gene. In clinical studies, low level GGT elevations during treatment were common, mild, and typically lasted longer than ALT/AST elevations. Bilirubin levels in patients experiencing transaminase or GGT elevations due to treatment with bardoxolone methyl either remained at baseline levels or decreased. The ALT, AST, and GGT elevations were generally self-limiting in patients who continued treatment with study drug.

### 2.4.1.3 Muscle Spasms

Muscle spasm was the most frequently reported adverse event in clinical trials of bardoxolone methyl in patients with CKD who also had type 2 diabetes. The muscle spasms most often manifested in the first two months of treatment and resolved spontaneously or with empirical treatment. They occurred mostly at night, in the lower extremities, and were generally mild to moderate in severity. Muscle spasms may result from improved insulin sensitivity and glucose uptake in skeletal muscle cells. Increases in glucose uptake, as assessed by the hyperinsulinemic-euglycemic clamp procedure, were observed in response to bardoxolone methyl in a defined subset of patients enrolled in a Phase 2a study. Clinical signs and laboratory findings associated with the reports of muscle spasms have not been consistent with muscle toxicity. Bardoxolone methyl subjects showed no increase in prominent laboratory findings associated with muscle toxicity, such as increased levels of serum markers, including creatinine, creatine kinase, lactate dehydrogenase (LDH), BUN, uric acid, phosphorus, and potassium.

### 2.4.2 Known Potential Benefits

As seen in Table 1, improvements in kidney function, including eGFR, creatinine clearance, and inulin clearance, have been observed with bardoxolone methyl treatment in multiple clinical studies, including patients with CKD, cancer, and pulmonary hypertension (PH). Bardoxolone methyl was originally considered for development in cancer patients, and in two Phase 1 studies, bardoxolone methyl was observed to reduce serum creatinine levels, corresponding to an increase in eGFR (Hong, 2012). The reductions of serum creatinine concentrations and resultant increases in eGFR were time-dependent and manifested in a majority (82%) of the patients studied. In subsequent studies that enrolled over 2600 patients with type 2 diabetes and CKD, bardoxolone methyl has been shown to consistently produce clinically and statistically significant improvements in eGFR that are durable for at least one year in treated patients (Chin, 2018; Pergola, 2011). The change in serum creatinine was not related to a reduction in creatinine generation (Chertow, 2018); improved kidney function was confirmed in a study of Japanese patients with type 2 diabetes wherein GFR was measured using inulin clearance, as well as estimated, using conventional GFR estimating equations (Nangaku, 2020).

Most recently, bardoxolone methyl was shown to significantly increase eGFR in patients with CKD due to Alport syndrome, ADPKD, IgAN, T1D CKD, or FSGS (Pergola, 2019). The clinical activity of bardoxolone methyl in various forms of CKD with distinct etiologies suggests that the anti-inflammatory and anti-fibrotic effects of bardoxolone methyl target the common final pathway contributing to GFR loss in multiple forms of CKDs.

**Table 1: Cross-Study Comparison of Increases in eGFR, Inulin Clearance, and Creatinine Clearance with Bardoxolone Methyl Treatment**

Study	Phase/ Country	Study Population	# of Patients	Treatment Duration	$\Delta$ eGFR (mL/min/1.73m  ) 
CKD Studies					
402-C-0801 (Stratum 1) (open label)	2a/ US	Age $\geq$ Diabetic nephropathy	18, 60	28 days	6.7 (p<0.001)
402-C-0801 (Stratum 2) (open label)	2b/ US	Age $\geq$ Diabetic nephropathy	18, 20	56 days	7.2 (p<0.001) CrCl also sig. increased
402-C-0804 (BEAM)	2/ US	Age $\geq$ T2D and CKD	18, 227	52 weeks	8.6 at WK52 (p<0.001 vs PBO)
402-C-0902	2/ US	Age $\geq$ 18, T2D and CKD	131	85 days	6.5 (p<0.001)
402-C-0903 (BEACON)	3/ Global	Age $\geq$ T2D and Stage 4 CKD	18, 2185	Median: 7 months with 522 patients through Week 48	6.4 (p<0.001 vs PBO) CrCl also significantly increased

CONFIDENTIAL

This material is the property of the NYU School of Medicine and Langone Medical Center. Do not disclose or use except as authorized in writing by the study sponsor

402-C-1102	1/US	Age $\geq$ 18, 24 T2D and Stage 3b and Stage 4 CKD	56 days	9.0 (p<0.05)
RTA402-005 (TSUBAKI)	2/ Japan	Age $\geq$ 20, 108 T2D and Stage 3 and 4 CKD	16 weeks	6.6 (inulin GFR) (p=0.008 vs PBO)
402-C-1603	2/US	Age 12 to 65, 30 Alport Syndrome	48 weeks	10.4 (p<0.001)
402-C-1603	3/Global	Age 12 to 70, 157 Alport Syndrome	48 weeks	9.5 (p<0.001 vs PBO)
402-C-1702	2/US	Age 18 to 70, 31 ADPKD	12 weeks	9.3 (p<0.001)
402-C-1702	2/US	Age 18 to 70, 26 IgA Nephropathy	12 weeks	8.0 (p<0.001)
402-C-1702	2/US	Age 18 to 70, 28 T1D CKD	12 weeks	5.5 (p=0.02)
Non-CKD Studies				
402-C-0501	1/ US	Age $\geq$ 18, Advanced Solid Tumors or Lymphoid Malignancies	47 Median: 56 days	18.2 (p<0.0001)
402-C-0702	1/2/ US	Pancreatic Cancer	34 Median: 56 days	32.2 (p=0.001)
402-C-1302 (LARIAT)	2/ US	Age 18 to 75 PH (Baseline eGFR 82 mL/min/1.73 m  )	54  16 weeks	14.7 (p<0.001 vs PBO)

a Unless noted, data are mean eGFR changes from baseline for bardoxolone methyl patients and p-values are calculated from two-sided paired t-tests comparing eGFR change to 0.

b Number of patients enrolled in Cohorts 1 and 2.

### 3 Objectives and Purpose

#### 3.1 Phase 2

##### 3.1.1 Primary Objective

- To provide an initial assessment of the safety of bardoxolone methyl in COVID-19 patients when compared with matching placebo

#### 3.2 Phase 3

##### 3.2.1 Primary Objectives

- To determine whether bardoxolone methyl in COVID-19 patients increases the probability of recovery at Day 29 when compared with matching placebo
- To assess the safety of bardoxolone methyl in COVID-19 patients when compared with matching placebo

##### 3.2.2 Secondary and Exploratory Objectives

- To assess the effect of bardoxolone methyl on other endpoints including renal function when compared with matching placebo

##### 3.2.3. Safety Endpoints

The following safety endpoints will be assessed during the study:

CONFIDENTIAL

This material is the property of the NYU School of Medicine and Langone Medical Center. Do not disclose or use except as authorized in writing by the study sponsor

- All adverse events that are serious, unexpected, and have a reasonable possibility of having been related to the study drug
- All unexpected deaths

## 4 Study Design and Endpoints

### 4.1 Description of Study Design

This multi-center, double-blind, placebo-controlled, randomized Phase 2/3 trial will study the safety, tolerability, and efficacy of bardoxolone methyl in patients hospitalized with confirmed COVID-19. Phase 2 is designed to provide an early interim analysis for safety and will enroll approximately 40 patients. Phase 3 is designed to determine whether bardoxolone methyl increases the probability of recovery at Day 29 compared with matching placebo. In phase 3, approximately 360-400 additional patients will be enrolled.

Patients will be randomized using permuted block randomization in a 1:1 fashion to either once-daily administration of bardoxolone methyl (20 mg) or matching placebo. Randomization will be stratified by study center and invasive mechanical ventilation (i.e., mechanical ventilation with endotracheal intubation) use at baseline (yes or no).

Enrollment of patients  $\geq 70$  years of age may be limited (e.g., comprise no more than 10% of all randomized patients), pending safety review by the DSMB and executive committee. Treatment will be administered for the duration of hospitalization (until recovery), with an expected duration of 10 days. For patients who are still hospitalized for more than 10 days, treatment can be continued for a maximum treatment duration of 29 days. Dose de-escalation (down to 10 mg) is permitted during the study if indicated clinically, and subsequent dose re-escalation is also permitted. Once a patient's dose has been reduced, dose re-escalation back to a higher dose is permitted.

Randomization will be performed using an interactive web response system (IWRS). Following randomization on Day 1, patients will be assessed while hospitalized on Days 3, 5, 8, 11, 15, 22, and 29. Assessments will include clinical status assessments, vital sign measurements, clinical chemistry collection, and adverse event collection. Patients that recover prior to Day 29 will complete an end-of-treatment visit. Patients will have an in-person follow-up on Day 29, regardless of treatment adherence and recovery status prior to Day 29, and a safety follow-up 60 days after randomization for clinical status assessments, vital sign measurements, clinical chemistry collection, and adverse event collection. Follow-up in-person visits are preferred but recognizing quarantine and other factors may limit the subject's ability to return to the site for the visit. In this case, the visit may be performed by phone. An independent Data and Safety Monitoring Board (DSMB) will advise the study leadership on safety aspects and overall progress of the study.

The phase 2 primary endpoint will be assessed during the treatment phase, defined as while hospitalized and up to Day 15. The phase 3 primary endpoint will be assessed during the treatment phase, defined as while hospitalized and up to Day 29. Enrollment of the phase 3 cohort will initiate after safety and proof of concept has been confirmed in the Phase 2 cohort.

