
Description of Study Agent/Procedure
	
Bardoxolone methyl will be administered orally at 20 mg once daily. Patients unable to receive oral dosing will receive study drug via a nasogastric or orogastric tube.

CONFIDENTIAL

[figure not shown]
This material is the property of the NYU School of Medicine and Langone Medical Center. Do not disclose or use except as authorized in writing by the study sponsor

Reference Therapy	Placebo
Statistical Analysis	
A total sample size of approximately 400 participants (Phase 2 combined with Phase 3, or Phase 3 alone) randomized 1:1 using permuted block randomization (~200 bardoxolone methyl; ~200 placebo) is expected to provide approximately 80% power at a two-sided 0.05 significance level using a generalized linear model analysis to detect a risk difference of +14%, assuming the following:
 
 
• Follow-up for events for 28 days after randomization (through Day 29)
 
• 2% of patients in each group drop-out prior to recovery
 
• Recovery for 50% patients randomized to placebo relative to 64% of patients randomized to bardoxolone methyl.
 
 
At a designated time during the trial (~40% and ~70% of projected sample size has accrued) interim analysis will be performed for safety, harm, and futility.
 
The analysis will be based on intention to treat using a generalized linear model analysis to compare the probability of recovery at Day 29. The phase 2 analysis for safety will not assess the primary endpoint and will not impact the overall type I error rate of the trial. If the DSMB concludes the trial should continue to the Phase 3 part, then the phase 2 patients will be included in the phase 3 portion of the study (unless Phase 2 is unblinded as discussed in Section 8.6).

CONFIDENTIAL

This material is the property of the NYU School of Medicine and Langone Medical Center. Do not disclose or use except as authorized in writing by the study sponsor

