### 4.2.2.1 Primary Efficacy Endpoint

- Proportion of subjects recovered (defined as alive, free of respiratory failure [e.g., need for non-invasive or invasive mechanical ventilation, high flow oxygen, or ECMO], and free of renal replacement therapy [RRT]) at Day 29.

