### **10.2.2 Phase 3**

All statistical hypotheses will be tested using a two-sided significance level of 0.05. The Phase 3 primary outcome is recovery at Day 29. The key parameter of interest is the “risk difference,” which quantifies the shift in probability of recovery resulting from treatment. A positive risk difference 1 indicates a higher proportion of patients recovering in the bardoxolone methyl group relative to placebo. The null hypothesis to be tested is that the risk difference is the same for the placebo and bardoxolone methyl arms and is stated as  $H_0: RD = 0$ , where RD denotes the risk difference.

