### **10.4.2 Analysis of the Phase 3 Primary Efficacy Endpoint**

The primary efficacy endpoint is recovery, where recovery is defined as meeting all of the following criteria at Day 29:

- Alive,
- Free of respiratory failure, and
- Free of renal replacement therapy (RRT).

Analysis of the Phase 3 primary endpoint will occur after the last patient enrolled has been followed up to Day 29 and the study is complete. The analysis will be based on the test of treatment effect estimated from a generalized linear model analysis accounting for the stratification factors of study center and mechanical ventilation status as covariates. The primary efficacy endpoint will be a covariate-adjusted estimate as specified in the Statistical Analysis Plan. Events will be analyzed and presented as summary tables of proportion recovered with risk differences and 95% confidence intervals (CIs) for the comparison of

CONFIDENTIAL

This material is the property of the NYU School of Medicine and Langone Medical Center. Do not disclose or use except as authorized in writing by the study sponsor

bardoxolone methyl to placebo. The SAP will include additional detail of the planned analyses and definitions of sensitivity analyses.

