## 10.5 Sample Size

A total sample size of approximately 400 participants (Phase 2 combined with Phase 3, or Phase 3 alone, depending on unblinding of Phase 2) randomized 1:1 using block randomization (~200 bardoxolone methyl; ~200 placebo) is expected to provide approximately 80% power at a two-sided 0.05 significance level using a generalized linear model analysis to detect a risk difference of +.14, assuming the following:

- Follow-up for events for 28 days after randomization (at Day 29)
- 2% of patients in each group drop-out prior to Day 29
- Increase in the probability of recovery from 50% for patients randomized to placebo relative to 64% of patients randomized to bardoxolone methyl.

Under these assumptions, approximately 228 (57% of the 400 enrolled) will have recovered at Day 29. The primary analysis will be based on the ITT population. The secondary endpoints will be tested using a strategy that preserves the overall Type I error rate. Analysis of the primary endpoint will occur after the last patient enrolled has been followed to Day 29. The phase 2 analysis for safety will not assess the primary endpoint and will not impact the overall type I error rate of the trial. If the DSMB concludes the trial should continue to the Phase 3 part, then the phase 2 patients will be included in the phase 3 portion of the study.

Table 5 shows effects detectable with 80% power for a total sample size of 400 and a range of proportion of placebo patients recovered at Day 29.

**Table 5. Effects detectable with 80% power for a sample size of n=400 and a range of proportion of placebo patients recovered**

Placebo Proportion Recovered at Day 29	Bardoxolone Proportion Recovered at Day 29	Risk Difference
0.350	0.488	0.14
0.400	0.539	0.14
0.450	0.590	0.14
0.500	0.638	0.14
0.550	0.686	0.14
0.600	0.732	0.13
0.650	0.776	0.13
0.700	0.819	0.12
0.750	0.861	0.11
0.800	0.900	0.10
0.850	0.936	0.09
0.900	0.969	0.07

CONFIDENTIAL

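### Section 4.1 ties the Phase 3 primary endpoint to time in hospital, while the rest of the plan defines it as status at Day 29 in every patient; one sentence should be corrected

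*Combined protocol and SAP*

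**What the plan says.** Section 4.1, last paragraph, gives the assessment window: "The phase 3 primary endpoint will be assessed during the treatment phase, defined as while hospitalized and up to Day 29". The same section says that treatment runs for the hospitalization, until recovery, with an expected duration of 10 days and a maximum of 29.

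Four other sections fix the endpoint at Day 29 without reference to being in hospital:

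- 4.2.2.1: alive, free of respiratory failure "and free of renal replacement therapy [RRT]) at Day 29".
- 10.2.2: "The Phase 3 primary outcome is recovery at Day 29".
- 10.4.2: "where recovery is defined as meeting all of the following criteria at Day 29".
- 10.5: "approximately 228 (57% of the 400 enrolled) will have recovered at Day 29".

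The visit plan agrees with these four. One paragraph before the disputed sentence, 4.1 says: "Patients will have an in-person follow-up on Day 29, regardless of treatment adherence and recovery status prior to Day 29". Section 7.1.1.9 allows that contact by telephone. Section 7.2.2.8 arranges an outpatient visit for patients discharged earlier and lists the recovery assessment there. Table 1 in section 19, with footnote k, schedules it for everyone.

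The drop-out assumption also appears in two forms. The Protocol Summary (Statistical Analysis) has "2% of patients in each group drop-out prior to recovery"; section 10.5 has "2% of patients in each group drop-out prior to Day 29".

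**The concern.** The trial has one primary efficacy endpoint, so it should have one assessment time. The 4.1 sentence is worded as a definition, and for a patient who goes home around the expected 10 days its window closes well before Day 29. A patient discharged in good condition who then dies at home, or who is on outpatient RRT or home ventilatory support at Day 29, is not recovered under 4.2.2.1 and 10.4.2 but falls outside the 4.1 window.

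The difference has a practical side. Recovery status is recorded both at the End of Treatment visit (7.2.2.9) and at Day 29 (7.2.2.8), so either version could be derived from the database. Section 10.1 makes a separate, later SAP the final arbiter of the analyses, and the protocol should hand that SAP a single rule.

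**Working it through.** **1. The plan's own figures (10.5).** Inputs: 50% vs 64% recovered, two-sided alpha 0.05, power 80%, 2% drop-out, 1:1 allocation.

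- Pooled proportion = (0.50 + 0.64)/2 = 0.57.
- n per arm = [1.960·√(2·0.57·0.43) + 0.842·√(0.50·0.50 + 0.64·0.36)]² / 0.14² = 195.1, rounded up to 196.
- Total = 392; 392/0.98 = 400, as stated.
- Power at 196 per arm is 80.2% (pooled). Unpooled: SE = √(0.4804/196) = 0.0495, and Φ(0.14/0.0495 − 1.96) = 0.807.
- Expected recoveries = 200·0.50 + 200·0.64 = 228, as stated.

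The sample size therefore already uses status at Day 29. Aligning 4.1 with it changes none of these figures.

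**2. Who is classified differently.**

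| Patient discharged before Day 29 | Status-at-Day-29 sections | 4.1 read literally |
|---|---|---|
| Alive and off support at Day 29, even after an interim relapse | Recovered | Recovered |
| Readmitted, in respiratory failure or on RRT in hospital at Day 29 | Not recovered | Arguably inside the window, because hospitalized again |
| Died outside hospital by Day 29 | Not recovered | Outside the window |
| Outpatient RRT or home ventilatory support at Day 29 | Not recovered | Outside the window |

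Only the last two rows clearly separate the texts.

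**3. A ceiling on the count.** Let d be the share of all patients discharged early, and r the share of those who are dead, in respiratory failure or on RRT at Day 29. Neither is in the documents. Early-discharged patients still recovered at Day 29 cannot exceed all recoveries, so 400·d·(1 − r) ≤ 228. Hence the number failing is 400·d·r ≤ 228·r/(1 − r).

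| Assumed r | Ceiling (patients of 400) |
|---|---|
| 0% | 0 |
| 1% | 2.3 |
| 2% | 4.7 |
| 4% | 9.5 |
| 8% | 19.8 |

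These values overstate the disagreement. They include readmitted patients, and any patient already on RRT at discharge, who is not recovered under either reading.

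**4. Drop-out wording.** 2% of 400 is 8 patients in both places. The wordings differ only for a patient lost between recovery and Day 29, who counts as a drop-out in 10.5 but not in the Summary.

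**5. Separate illustration: a baseline covariate.** With 392 evaluable patients, center assumed not prognostic, and strata k with weight w_k, rates p0k and p1k and difference RD_k:

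Var = (1/392)·{Σ w_k·2[p1k(1 − p1k) + p0k(1 − p0k)] + Σ w_k(RD_k − 0.14)²}; power = Φ(0.14/√Var − 1.96).

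All stratum values below are assumed, for ordinal categories 4 / 5 / 6 / 7 and above, and chosen to give 50% vs 64% overall.

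| | Flat gradient | Steep gradient |
|---|---|---|
| Weights (%) | 10 / 30 / 35 / 25 | 15 / 35 / 35 / 15 |
| Placebo | 0.711 / 0.613 / 0.514 / 0.260 | 0.85 / 0.65 / 0.35 / 0.15 |
| Bardoxolone methyl | 0.823 / 0.749 / 0.666 / 0.399 | 0.921 / 0.793 / 0.526 / 0.267 |
| Ventilation only: bracket, power | 0.884, 0.839 | 0.869, 0.845 |
| With categories 4, 5, 6: bracket, power | 0.872, 0.843 | 0.766, 0.886 |
| Variance reduction | 1.3% | 11.8% |

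**The case against.** The strongest reply is that the plan already answers the question. The Protocol Summary, the endpoint section, the hypotheses, the analysis section, the sample size and the schedule all say Day 29, and 4.1 itself requires Day 29 follow-up of everyone. The telephone contact in 7.1.1.9 asks about hospital visits, continuing care and death, so events outside hospital would be picked up. On this view the sentence is a loose description of an observation period. Much of that stands: the weight of the text favors Day 29, and the correction is small. It does not remove the conflict, because the sentence gives an explicit definition that leaves out the very patients 7.2.2.8 brings back.

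Two further replies also stand. The sentence does not say index hospitalization, so a readmitted patient is arguably covered. And it would be wrong to say that the recovery visit is undefined: 7.1.1.12 lists the same three components, and 7.2.2.9 applies that assessment at End of Treatment.

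A reader might go further and infer that End of Treatment status would replace Day 29 status in the analysis. No section says so. A reader might also infer that power is lost because 50% and 64% could be rates at discharge. Section 10.5 places the resulting 228 recoveries at Day 29, so the documents do not support that either.

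**Conclusion.** The contradiction is real and should be corrected, but it is one of wording about the endpoint's timing and does not threaten the design. Read literally, 4.1 would miss mainly deaths outside hospital and outpatient RRT or home ventilatory support at Day 29. It would not clearly miss every post-discharge failure.

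The number of patients cannot be derived from the documents. The range of 2.3 to 19.8 of 400 is a ceiling that rests wholly on an assumed r of 1% to 8%. It counts patients classified differently. Someone might read a bias in the treatment difference into it, but nothing in the documents gives r by arm, and no such shift is claimed. N = 400, about 80% power and 228 expected recoveries are unaffected.

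The drop-out mismatch is a matter of alignment only. The covariate suggestion corrects no error; its gain of 0.4 to 4.1 percentage points of power depends on the assumed case mix.

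**What to change.** - **Section 4.1:** replace the sentence with *The Phase 3 primary endpoint is status at Day 29 in all randomized patients, irrespective of discharge or treatment discontinuation.*
- **Protocol Summary, Statistical Analysis:** count the 2% drop-out to Day 29, as in 10.5. The 2% and N = 400 stay as they are.
- **Use of the word recovery:** the sponsor should reconcile its use for treatment duration (4.1, 6.1.9) with the three-component definition (7.1.1.12, 10.4.2). This is more than editing, because patients eligible under 5.1 on infiltrates alone or on low-flow oxygen can already meet the three components at entry. No clinical rule is proposed here.
- **Optional, separate:** in the SAP's primary model, add baseline ordinal clinical status (categories 4, 5 and 6 among patients not on invasive ventilation) to center and ventilation, with the ventilation term covering category 7 and above.

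Cost: one protocol sentence, one phrase in the Summary, a wording reconciliation and, if adopted, one covariate. Recovery status is already scheduled at Day 29, and clinical status at Screening and Day 1, so no patients or visits are added.
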